7.3 Safety Population

The Safety Population will include all subjects who receive at least 1 dose of the study drug.

7.4 Full Analysis Set (FAS)

The FAS includes all the patients who sign the Informed Consent Document and are enrolled into the study. This set will be used for reporting patient demographic data and any available patient baseline characteristics as captured in the Case Report Form (CRF).

Membership in the analysis populations will be determined before database lock.

8. Randomization and Blinding

This is a non-randomized, open label study.

9. Method of Analysis

9.1 Statistical Hypotheses

There are no formal statistical hypotheses.

9.2 Interim Analysis

After all patients enrolled in Part 1 have had the opportunity to provide at least three tumor outcome assessments, the DRC will evaluate the efficacy (anti-tumor activity) and safety results for each of the subtypes. If the committee believes there are potential clinically meaningful responses for certain subtype, the committee will recommend initiation of Part 2 to evaluate efficacy and safety for that subtype. Else, the study will be terminated.

The DRC will continue to monitor safety of Tenalisib (or toxicity trends that may be of concern) at interval of approximately 3 months from initiation of study until the completion of the study. In the event of one (1) death attributed to the study drug, study accrual will be suspended pending

further investigation, and will only be resumed at the recommendation of the DRC. The DRC will have discretion to terminate the trial if an additional death occurs that can be attributed to the study drug.

9.3 Handling of Missing Data

9.3.1 Missing Dates for Adverse Events and Concomitant Medications

Adverse events and concomitant medications with completely or partially missing assessment dates will have imputation performed as explained below for the purposes of calculation of durations or relativity to study medication.

For the end of a concomitant medication or adverse event:

- **If only Day of end date is missing:**

The last date of the month and year reported or the date of the final contact with the subject, whichever is earlier, will be used as the end date.

- **If Day and Month of end date are missing:**

The last date of year i.e. December 31 of the year reported or the date of the last study contact with the subject, whichever is earlier, will be used as the end date.

- **If Year of end date or complete end date is missing:**

If the year of end of medication/event is missing or end date is completely missing, then no end date will be imputed.

For the start of a concomitant medication or adverse event:

- **If only Day of start date is missing:**

- If the start year and month of medication/event are the same as that for the first dose date, then following approach will be used:

- If the end date of medication/event is NOT before the first dose date or end date of medication/event is completely missing, then impute the start day as the day of first dose date
- Otherwise, impute the start day as 1.

- If the start year and month of medication/event are NOT same as that for the first dose date, then

- Impute the start day as 1.

- **If Day and Month of start date are missing:**

- If start year of medication/event is same as first dose year, then following approach will be used:

- i. For medication, impute the start Month as January and the Day as 1

- ii. For adverse event,
 - If the end date of event is NOT before the first dose date or end date of event is completely missing, then impute the start Month and Day as the Month and Day of first dose date;
 - Otherwise, impute the start Month as January and the Day as 1.
- If start year of medication/event is NOT same as first dose year, then
 - Impute start Month as January and the Day as 1.
- **If Year of start date or complete start date is missing:**

If the year of start of medication/event is missing or start date is completely missing, then no start date will be imputed.

9.3.2 **Missing Dates for Efficacy Endpoints**

For time-to-event endpoints (Progression Free Survival, Overall Response and Duration of response), if the date is completely missing, no imputation will be performed.

However, the incomplete/partial dates will be handled following the general conventions as detailed in Section 9.3.1.

Patient without measurable and/or assessable lesions will not be assessed for response.

Measurable lesions are defined as those that can be accurately measured in at least two dimensions with conventional techniques (CT/PET/PET-CT, MRI, x-ray) or as >1.5 cm with CT scan.

9.3.3 **Missing dates for Primary Diagnosis/Prior therapy**

Partial Primary diagnosis and prior therapy dates will have imputation performed as explained below for the purposes of calculation of relativity to study medication.

- If only Day is missing, impute the day 1
- If Day and Month are missing, impute the Month as January and the Day as 1.
- If the year of primary diagnosis is missing or the date of primary diagnosis is completely missing, then no date will be imputed.

10. **Statistical Analysis**

Due to early closure of the study, the analysis proposed in the SAP is based on the available data at the time of study closure.

The safety endpoints will be listed and/or summarized. No inferential statistical analyses will be performed.

Unless otherwise stated, all statistical analyses will be performed using a two-sided hypothesis test at the overall 5% level of significance.

When count data are presented, the percentage will be suppressed when the count is zero in order to draw attention to the non-zero counts. A row denoted “Missing” will be included in count tabulations where necessary to account for dropouts and missing patients. Unless otherwise specified, the denominator for percentages will be the number of patients with a non-missing assessment in a given treatment group within the analysis population of interest.

All statistical analyses will be performed using SAS 9.4 or higher.

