#### **4.2 Exclusion Criteria**

1. Histologically confirmed diagnosis of follicular lymphoma grade 3b or transformed disease or chronic lymphocytic leukemia (CLL).
2. Patients receiving cancer therapy (i.e., chemotherapy, radiation therapy, immunotherapy, biologic therapy, hormonal therapy, surgery and/or tumor embolization) or any cancer investigational drug within 3 weeks (21 days) or 5 half-lives (whichever is shorter) prior to C1D1. Corticosteroids (prednisone or equivalent) at a dose of < 20 mg daily are allowed. Corticosteroid should be stabilized for at least 1 week prior to C1D1.
3. Autologous hematologic stem cell transplant (Auto-SCT) within 3 months from C1D1. Patients must not have active graft versus-host disease;
4. History of an allogeneic bone marrow transplant (Allo-SCT)
5. Active hepatitis B or C infection. (All subjects must be screened for hepatitis B and C up to 28 days prior to C1D1 using the hepatitis viral panel. Subject positive for HBsAg or HBcAb will be eligible if they are negative for HBV-DNA. Subject positive for HCV IgG will be eligible if they are negative for HCV-RNA);
6. Known history of human immunodeficiency virus (HIV) infection;
7. Evidence of ongoing severe systemic bacterial, fungal or viral infection;
8. Known primary central nervous system lymphoma or known intracranial involvement, leptomeningeal metastases or spinal cord compression due to disease or any preexisting neurologic manifestations;
9. Known history of severe drug-induced liver injury, alcoholic liver disease, primary biliary cirrhosis, ongoing extrahepatic obstruction caused by stones, cirrhosis of the liver or portal hypertension;
10. Patient with any severe and/or uncontrolled medical conditions or other conditions that could affect their participation in the study as per investigator's judgement;
11. Patient with symptomatic, or history of documented congestive heart failure (NY Heart Association functional classification III-IV);
12. Patient with angina not well-controlled by medication;
13. Patient with poorly controlled or clinically significant atherosclerotic vascular disease (including cerebrovascular accident, transient ischemic attack or have angioplasty, cardiac or vascular stenting) in the past 6 months;
14. Prior exposure to drug that specifically inhibits PI3K (e.g. Idelalisib, Copanlisib, Duvelisib and Umbralisib);

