10.2 Demographic and Baseline Characteristics

Analysis set: FAS

Demographic and baseline characteristics data will be summarized using descriptive statistics (n, mean, Standard Deviation, median, minimum, maximum) for continuous variables, and using frequencies and percentages for categorical variables.

Demographic characteristics will include age, race, gender, height, weight, etc.

Disease characteristics will include time from initial diagnosis to enrollment, Subtype of iNHL, Staging, number of prior therapies, (systemic therapy, radiotherapy and cancer surgery), number of subject relapsed or refractory to the last therapy, time from date of last therapy to enrollment, ECOG performance status, etc.

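### SAP 9.3.3 gives partial start and end dates of prior therapy the same first-of-period rule, so an imputed end can precede its recorded start and time since last therapy can only be lengthened

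*SAP*

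**What the plan says.** SAP 9.3.3 states its scope as follows: "Partial Primary diagnosis and prior therapy dates will have imputation performed as explained below for the purposes of calculation of relativity to study medication". The rules are "If only Day is missing, impute the day 1" and "If Day and Month are missing, impute the Month as January and the Day as 1". Start and end of a therapy are not distinguished, and nothing requires the imputed end to fall on or after the start. The bullet for a missing year names only the primary diagnosis: "If the year of primary diagnosis is missing or the date of primary diagnosis is completely missing, then no date will be imputed".

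SAP 9.3.1, on adverse events and concomitant medications, does separate the two. With only the day missing, it sets an end date to "The last date of the month and year reported or the date of the final contact with the subject, whichever is earlier". With day and month missing, it uses 31 December with the same kind of cap.

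SAP 10.2 lists "time from date of last therapy to enrollment" among the disease characteristics summarised in the FAS. It does not say whether the date meant is the start or the end of that therapy.

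**The concern.** A first-of-period rule is a common choice for a start date. For an end date it picks the earliest day consistent with the record, and two things follow.

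- **Order.** If the start is recorded more completely than the end, the imputed end can come before the start. The recorded start alone then shows the derived date to be wrong.
- **Direction.** An end date moved earlier lengthens the time since last therapy. The errors share one sign, so they do not average out across patients.

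What is at stake is one row of the baseline table, which helps a reader judge how recently these patients, with at least two prior lines, were last treated. Partial dates are plausible, because Protocol 6.2.5 collects all prior cancer treatment back to initial diagnosis. The documents do not say how many dates are partial.

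**Working it through.** The plan gives no figure on this point, so there is none to reproduce. The inputs are the two 9.3.3 rules, the 9.3.1 end-date rule, the 10.2 interval, and the planned 20 patients (SAP 6). Three assumptions are mine: the date of last therapy is the end date, the imputed date feeds 10.2, and true dates are uniform over a 365-day year.

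**1. Size of the overstatement (true end minus imputed end)**

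- Day missing: in a month of L days the error runs from 0 to L − 1. The mean over the year is the sum of L(L − 1)/2 over months, divided by 365: (7 × 465 + 4 × 435 + 378)/365 = 5373/365 = 14.7 days. The range is 0 to 30.
- Day and month missing: the error runs from 0 to 364, with mean 364/2 = 182 days (maximum 365 in a leap year).
- The error is never negative. It is zero when the true day is the 1st of the month (12/365 = 3.3% of days) or, for a year-only date, 1 January.

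**2. End before start**

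Take a start of 15 March 2018 and an end recorded only as 2018. The imputed end is 1 January 2018, which is 31 + 28 + 14 = 73 days before the start.

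How often this happens depends on the time from start to end, with a complete start date:

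| Start to end | End day missing | End day and month missing |
|---|---|---|
| 14 days | 51% | 96% |
| 28 days | 5% | 92% |
| 84 days | 0% | 77% |
| 168 days | 0% | 54% |

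The last column is (364 − length)/365; for 28 days, 336/365 = 92%. If start and end lack the same parts and fall in the same month or year, the two imputed dates coincide and are not reversed.

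**3. Effect on the reported mean**

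With 20 patients, one year-only end date moves the mean by 182/20 = 9.1 days on average and by at most 364/20 = 18.2 days. It could also set the reported maximum.

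**4. What other conventions would do**

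Keep the example in step 2 and assume enrollment in 2019. The true end lies between 15 March (day 74) and 31 December (day 365), with mean day (74 + 365)/2 = 219.5. A positive error means that time since therapy is too long.

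| Imputed end | Error range, days | Mean error, days |
|---|---|---|
| 1 January (9.3.3 as written) | +73 to +364 | +218.5 |
| 15 March (recorded start as floor) | 0 to +291 | +145.5 |
| 7 August (midpoint of window, day 219) | −145 to +146 | +0.5 |
| 31 December (9.3.1 convention) | −291 to 0 | −145.5 |

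The floor alone is better than the rule as written for every possible true date in this example. The 9.3.1 convention restores the order but reverses the bias. Without a recorded start, its understatement has the same means as in step 1, 14.7 and 182 days.

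**The case against.** The strongest reply is that little depends on this. The SAP has no formal hypotheses, the study closed for lack of meaningful response, and ORR, CR rate, PFS and DoR do not use prior-therapy dates. SAP 10.2 reports relapsed or refractory status to the last therapy separately, so this interval is not the main measure of refractoriness. All of that stands, and it is why the point is minor.

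A second reply is that 9.3.1 imputes for durations as well as timing, while 9.3.3 names only timing relative to study medication. No duration of prior therapy is planned, so a reversed pair of dates enters no reported summary. This stands in part. The 10.2 interval is nevertheless a length of time, and its value depends directly on where the end date is placed.

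A third reply is that the 9.3.1 rule only exchanges one bias for another. That is correct, and simply importing it is not enough.

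A reader might also infer that imputed dates could make a patient who failed the washout look eligible and so distort the per-protocol set. The documents do not support this:

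- Exclusion 2 is judged before C1D1, and Protocol 6.2.4 and 6.2.5 have the investigator review prior medication, washout requirements and prior cancer treatments.
- No SAP section computes washout or eligibility from imputed dates. Under SAP 11 the medical monitor reviews deviations and decides per-protocol inclusion.
- The criterion reads "within 3 weeks (21 days) or 5 half-lives (whichever is shorter) prior to C1D1", so a gap under 21 days is not in itself a violation.

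**Conclusion.** The point holds at minor severity. As written, SAP 9.3.3 can place the end of a therapy before its recorded start. When the end date is partial, the 10.2 interval is never too short and usually too long: by 0 to 30 days (mean about 15) with the day missing, and by 0 to 364 days (mean about 182) with day and month missing.

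It would go too far to say that the interval is always too long. Complete dates are unaffected, and a partial date whose true value is the first of its period has no error.

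The means rest on uniform true dates, and the link to 10.2 rests on reading the date of last therapy as the end date. They are sizes per partial date. The effect on the reported summary depends on how many last-therapy dates are partial, which is not given.

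**What to change.** In SAP 9.3.3:

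- Keep day 1 and January for primary diagnosis and therapy start dates.
- For a partial therapy end date, impute within the recorded month or year, no earlier than that therapy's recorded start and no later than the earlier of enrollment and the day before first dose. Both upper limits are needed: with a cap at the day before first dose alone, enrollment could precede the imputed end and the interval would be negative.
- Name the value taken within that window: its midpoint, or the 9.3.1 end-date convention with a statement that the remaining error makes the interval too short.
- While the section is open, say what happens when the year of a prior therapy is missing.

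In SAP 10.2, state that the date of last therapy is its end date.

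The cost is a few lines of text and one programming condition. Reported time since last therapy will be somewhat shorter for patients with partial end dates, and under the 9.3.1 option it may be understated.

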10.1 Patient Disposition

A tabular presentation of the patient disposition data will be provided. It will include the number of patients screened, enrolled, assigned treatment, completed, as well as the number of dropouts, with reasons for discontinuation, number in each population sets, number of patients with dose reductions or interruptions (if applicable), etc. All patients’ data will be used for this report.

10.2 Demographic and Baseline Characteristics

Analysis set: FAS

Demographic and baseline characteristics data will be summarized using descriptive statistics (n, mean, Standard Deviation, median, minimum, maximum) for continuous variables, and using frequencies and percentages for categorical variables.

Demographic characteristics will include age, race, gender, height, weight, etc.

Disease characteristics will include time from initial diagnosis to enrollment, Subtype of iNHL, Staging, number of prior therapies, (systemic therapy, radiotherapy and cancer surgery), number of subject relapsed or refractory to the last therapy, time from date of last therapy to enrollment, ECOG performance status, etc.

10.3 Medical and Surgical History

Analysis set: FAS

This data will be summarized using frequencies and percentages by System Organ Class and Preferred Term. A listing will also be provided.

The medical history data will be coded using MedDRA dictionary [Version 23.0 (Hierarchy)].

10.4 Prior and Concomitant Medications

Analysis set: FAS

Concomitant medications are those that were taken while on study drug. Also, the medications / non-drug treatments which start after study treatment end date will be termed as ‘Concomitant’.

Prior medications are those that were taken prior to the initial dose of study drug.

The medication data will be coded using WHO-Drug dictionary (WHODRUG GLOBAL B3 March 1, 2020) and the non-drug treatments data will be coded using MedDRA dictionary [Version 23.0 (Hierarchy)].

A summary of frequencies and percentages by ATC level 2 and Preferred Terms and the listing of the prior and concomitant treatments taken will be provided.

10.5 Efficacy Analysis

Analysis Set: mITT and PP

- The analysis will be done as per the disease subtypes [Follicular lymphoma (FL), Marginal zone lymphoma (MZL), Waldenstrom's macroglobulinemia (WM) and Small lymphocytic lymphoma (SLL)] and overall.

Note: The analyses outlined below are subject to availability of adequate data. In absence of adequate data, some of the efficacy endpoints discussed below will be presented with basic summaries and/or plots and listings, as appropriate.

10.5.1 Objective Response Rate (ORR)

It is defined as sum of CR and PR rates. Only those patients who have had a pre-treatment baseline efficacy evaluation and at least one post-treatment efficacy evaluation or confirmed disease progression will be considered evaluable for response. [Subtype specific](#) and overall ORR will be calculated.

Additionally, Disease Control Rate (DCR= CR+PR+SD) will be presented.

This data will be summarized using frequency, and percentage. Due to low number of patients observed in each of the disease subtype, the 95% CI (Using exact method based on binomial distribution, subject to availability of adequate data) will be presented for the Overall group only.

The corresponding listing will also be provided.

10.5.2 Complete Response (CR) Rate

For assessment of CR, only those patients who have had a pre-treatment baseline efficacy evaluation and at least one post-treatment efficacy evaluation or confirmed disease progression will be considered evaluable for response.

This data will be summarized using frequency, and percentage. Due to low number of patients observed in each of the disease subtype, the 95% CI (Using exact method based on binomial distribution, subject to availability of adequate data) will be presented for the Overall group only.

10.5.3 Progression Free Survival (PFS)

It is defined as time of the first dose of Tenalisib to disease progression or death. Subjects who die without a reported prior progression will be considered to have progressed on the date of their death. Subjects who did not progress or die will be censored on the date of their last tumor assessment.

This data will be summarized using the Kaplan-Meier method and displayed graphically per the [disease subtype](#) and Overall. The following reports will be generated:

- The Q1, median and Q3 PFS time will be provided. Due to low number of patients observed in each of the disease subtype, 95% CI for the Q1, median, and Q3 PFS time will be presented for the Overall group only using Brookmeyer-Crowley method subject to availability of adequate data.
- The number and % of patients with disease progressive events (further divided into progression or death) will be provided.
- The number and % of patients censored (further divided by reasons for censoring) will be provided.
- Kaplan-Meier curves will be produced.
- A listing of PFS data will be provided.

10.5.4 Duration of Response (DoR)

It is defined as the time when the measurement criteria are first met for PR or CR (whichever is reported first) until the date of documented disease progression or death. For subjects who neither progress nor die, the duration of response will be censored at the date of their last disease assessment.

This data will be summarized using the Kaplan-Meier method and displayed graphically per the [disease subtype](#) and overall. The following reports will be generated:

- The Q1, median, and Q3 DoR time will be provided. Due to low number of patients observed in each of the disease subtype, 95% CI for the Q1, median, and Q3 DoR time will be presented for the Overall group only using Brookmeyer-Crowley method subject to availability of adequate data.
- A plot of duration of response will be provided and include each responding patient (subject to availability of adequate data).

10.5.5 Best Overall Response

It is the best response recorded from the start of the treatment until disease progression or discontinuation from the study.

This data will be summarized using frequency and percentage for Complete Response (CR), Partial Response (PR), Stable Disease (SD), and Progressive Disease (PD), as captured in the CRFs, per the [disease subtype](#) and overall. This data will also be listed.

10.6 Safety Analysis

Analysis Set: Safety

The safety analyses will be reported for Overall patient data only. However, when necessary, adverse event data may be reported by [disease subtype](#).

10.6.1 Treatment Exposure and Compliance

Analysis set: Safety

Treatment compliance and the treatment exposure will be summarized descriptively (n, mean, median, standard deviation, minimum and maximum values) and will also be listed.

- The treatment exposure to the study medication for subject will be calculated as:
Exposure (day) = Last day of dosing – First Day of dosing + 1
 - A summary of duration of treatment (days) will be provided. In addition, a plot for duration on treatment will be provided per patient.
- The treatment compliance percentage (per patient), which is captured in the eCRF, will be summarized descriptively per Cycle. This data will be listed for individual patient.

